6. STUDY OBJECTIVES AND DESIGN

6.1 Overall Study Design (figure 1)

This study is a partially blinded, placebo-controlled cluster randomized trial of chemoprophylaxis to control outbreaks of COVID-19 in LCTHs for the elderly. The unit of analysis is a ward/unit. This design is selected to mimic the current approach to outbreaks of other respiratory viral infections, both because this approach has proven effective for these other viruses, and because it is standard practice and therefore feasible to implement.

Eligible LTCHs will be asked to report outbreaks to the study in addition to the legally-required reporting to their local public health unit; public health units will also be asked to discuss the study with LTCHs reporting outbreaks. In addition, study staff will contact the infection control practitioner in each of the screened LTCHs twice weekly, to ensure the prompt identification of outbreak units.

Either pre-study, or at baseline (identification of the outbreak), residents and staff will be assessed for contraindications to enrollment and informed consent will be obtained for residents and staff to receive the allocated intervention, and to be followed up individually for clinical outcomes, adherence and safety during the outbreak. Favipiravir or placebo will be offered to all residents and staff who will be working on the unit during the chemoprophylaxis period, according to the allocation. Surveillance for infection will occur as usual for resident illness within each facility; staff will be asked to report symptoms and will be screened for symptoms each time they enter the building. Consenting residents and staff will be screened at day 0, day 14 and day 40 to identify asymptomatic infections and to assess duration of viral shedding. The primary outcome will be control of the outbreak, defined as no new microbiologically confirmed case of COVID-19 for 24 consecutive days up to day 40.

STUDY SCHEME

1) Choose LTCH institutions for inclusion in the study for COVID19 screening 2) Identify Units with COVID19 outbreak (>=2 symptomatic and positive tested residents within a week) 3) Assess outbreak units for inclusion / exclusion. If qualifies-randomize unit to favipiravir or placebo (N=16 units) LTAC Institution 1 LTAC Institution 2 LTAC Institution 3 LTAC Institution 4 LTAC Institution 5 ITAC Institution 6 Unit 1 Unit 2 Unit 3 Unit 4 Unit 5 Unit 6 LTAC Institution 7 LTAC Institution 10 LTAC Institution 12 LTAC Institution 8 LTAC Institution 9 LTAC Institution 11 Unit 1 Unit 2 Unit 3 Unit 4 Unit 5 Unit 6 placebo favipiravir Unit 4 Unit 5 Unit 6 Unit 7 Unit 8 Unit 1 Unit 2 Unit 3 Unit 4 Unit 5 Unit 6 Unit 7 Unit 8 Unit 1 Unit 2 Unit 3 4) Chemoprophylaxis is continued for 25 days 5) On day 40 (15 days after end of prophylaxis): for each unit, determine control of the outbreak

Figure 1: a scheme of study flow.

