7.2.2 Exclusion criteria for LTCH Residents and Staff

- 1. Pregnancy (females < 55 years of age require a negative urine pregnancy test at enrollment, and either menopause or two concurrent reliable methods of contraception need to be confirmed)
- 2. History of abnormalities of uric acid metabolism, other than gout.
- 3. History of hypersensitivity to remdesivir or favipiravir
- 4. Previous diagnosis of hepatic cirrhosis
- 5. Current use of the following medications, which cannot be discontinued for the duration of the study: pyrazinamide, hydralazine, more than 3000 mg of acetaminophen per day

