7.3 Consent and Enrollment

The Medical Director, the LTCH Administrator and a delegate of the Residents' Council of the LTCH will give written informed consent for the LTCH to be included in the cluster trial. The LTCH Administrator will then delegate the personal distribution of a fact sheet describing the trial to all potentially eligible LTCH staff, residents and SDMs. The fact sheet will indicate that LTCH staff, residents and their SDMs would be contacted by research personnel in case of a COVID-19 outbreak in the LTCH, and offer them the possibility to opt out from being contacted by research personnel by calling or emailing the administration of the LTCH. In addition, posters about the trial will be placed in all staff locker rooms, lounges and nursing stations, and in public areas of the home.

LTCH staff, residents and their SDMs who did not opt out within 5 calendar days after receipt of the fact sheet will be contacted by research personnel. The study will be explained to each person, and written informed consent or e-consent will be obtained. This consent will include all features required for obtaining full informed consent, as outlined in the 2nd edition of the Tri-Council Policy Statement on Ethical Conduct of Research Involving Humans (TCPS2). LTCH staff and competent residents who provide written informed consent or e-consent at this stage may be enrolled into the trial. Residents who have been assessed as not competent to make their own medical decisions in their capacity evaluation

(https://collections.ola.org/mon/24004/300799.pdf) may be enrolled into the trial if their SDM provided written informed consent or e-consent.

For this trial, time to randomization and treatment is of considerable importance for outbreak control; thus, if written informed consent or e-consent has not been obtained prior to an outbreak being declared, informed consent will occur in two stages to minimize delays. LTCH staff, residents and/or their SDMs who have not opted out, but have not yet given written informed consent or e-consent, will therefore be asked to give preliminary consent by telephone or video call ≥24 hours after receipt of the fact sheet describing the trial. This consent will also include all features required for obtaining full informed consent, as outlined in the 2nd edition of

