the Tri-Council Policy Statement on Ethical Conduct of Research Involving Humans (TCPS2), ⁶⁶ and will be fully documented by the research personnel. Those who provide preliminary verbal consent at this stage may be enrolled into the trial. LTCH staff and competent residents who provide preliminary consent at this stage may be enrolled into the trial. Residents who are not considered competent to provide consent (see above) may be enrolled into the trial if their SDM provided preliminary consent. A second stage of the consent process in participants with preliminary consent will involve obtaining a signed copy of the REB-approved written informed consent form, either in electronic or hard copy, or e-consent. This stage should be done as soon as possible after the verbal preliminary consent is obtained, and research personnel will obtain a signed copy of the consent form or e-consent no later than 40 days after randomization

As new staff may be needed on the unit over time, any new staff starting work on the outbreak LTCH unit will be identified by the facility and referred to the trial for consenting and enrolment on an ongoing basis using the process described above.

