10.1.7 Additional Safety Considerations

For the purpose of this trial, the following are exclusion criteria for study drug administration:

- 1. Pregnancy
- 2. History of abnormalities of uric acid metabolism, other than gout.
- 3. Subject has a history of hypersensitivity to remdesivir or favipiravir
- 4. Known hepatic cirrhosis
- 5. Current use of the following medications, which cannot be discontinued for the duration of the study: pyrazinamide, hydralazine, more than 3000 mg of acetaminophen per day.

The following safety considerations are based on data from individuals taking favipiravir for influenza. They are listed here for reference.

- *Phototoxicity*: Nonclinical studies have shown mild phototoxicity. One study subject experienced mild photosensitivity (rash) following a tanning bed session. All subjects should avoid excessive exposure to sunlight or artificial ultraviolet light.
- *Laboratory Values*: Mild to moderate asymptomatic elevations of uric acid and aminotransferase have been observed in healthy volunteers and subjects with influenza treated with favipiravir in clinical studies. The changes have been reversible upon favipiravir discontinuation.
- *Mutagenesis:* Favipiravir proved mildly positive under some conditions studied in the mammalian chromosomal aberration test and mouse lymphoma assays at high concentrations. Although the potential for genotoxicity at high exposures cannot be ruled

- out, evidence indicates that this risk is minimal at the exposures planned in this clinical study.
- GI Tract Lesions: In two proof-of-concept studies of orally administered favipiravir against Ebola virus infection in macaques, GI tract lesions were observed that were not consistent with the known natural history of Ebola nor with previous animal and clinical studies of favipiravir. However, evidence suggests that bacterial infections and preexisting enterocolitis in the treated macaques may have been responsible, and an ongoing risk to patients may not exist.

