13.2 Screening, consenting and initial data collection Visit

The purpose is to rapidly assess participant eligibility and obtain written informed or preliminary verbal consent to participate in the trial, as eligibility and consent are required from at least 80% of residents on the outbreak ward in order to randomize. A nasopharyngeal or nasal swab will be obtained from all residents on day 0, and from all staff as soon as practical.

The study coordinator will:

- Review the patient's chart and medication record to assess eligibility; if possible, this will be performed remotely either via research staff having access to electronic charts, or by having a staff member in the home transmit the information by telephone or fax.
- If written informed consent has not yet been obtained, provide and review the informed consent document via email / fax / telephone / video link with each resident, substitute decision maker or staff person, and obtain and document verbal consent to participate.
- Advise the participant/substitute decision maker that written consent will be required as soon as possible and agree on the method by which this will be done.
- Provide contact information for the study, such that each participant has access to study personnel at any time to answer questions
- Obtain multiple forms of contact information for consenting participants, including multiple telephone numbers, an email address, and a mailing address for study material delivery.
- For study staff:
 - o Complete the baseline interview for study staff.
 - o Decide whether staff will complete daily diaries online or on paper
 - Review with the participant how to access and complete the symptom/adherence diary and questionnaires, and encourage immediate completion of the baseline questionnaire on the day of the visit.

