13.3 Medical Oversight

Confirmation of eligibility, assessment of adherence of study drug/placebo, evaluation of overall participant safety, review/assessment of minor and/or serious adverse events (including classification of adverse events according to seriousness, severity, relatedness and expectedness), and final sign off of data collection will be done by the qualified investigator/principal investigator ([name]) or a medically qualified and licensed delegated physician.

Table 1. Schedule of Events for Residents

Visit	Screening (Day 0)	Baseline (Day 1)	Day 14±2d	Day 40±4d	Day 60±7d
Visit format	Remote	Remote	In person	In person	Remote or
					in person
Eligibility	X				
assessment					
Informed consent	X				
Cluster		X			
randomization					
Dispensing study		X			
drugs					
Assessment for		Daily, by LT	ΓC staff (fax to	study)	
COVID-19		Chart review by	study staff, da	ay 14 & 40	
Concomitant medi-	X		X	X	
cation assessment					
Adverse event		Daily by LT	C staff (fax to	study)	SAE only
assessment		Chart review by study staff, day 14 & 40			
Death/hospital		Daily by LTC staff (fax to study)			X
transfer document.		Chart review by study staff, day 14 & 40			
Nasopharyngeal/	X		X	X	
nasal swab					
Medication			X	X	
adherence					

Table 2. Schedule of Events for Staff

Visit	Screening (Day 0)	Baseline (Day 1)	Day 14±2d	Day 40±4d		
Visit format	Remote or	Remote	Remote or in person	In person		
	in person*					
Eligibility	X					
assessment						
Informed consent	X					
Cluster		X				
randomization						
Dispensing study		X				
drugs						
Interview by study	X		X	X		
staff						
Concomitant medi-	X		X	X		
cation assessment						
Adverse event			X	X		
assessment						
Daily diary		Daily symptom/adverse event/adherence diary to be completed				
Visit-specific	X		X	X		
questionnaire						
Nasopharyngeal/	X^1		X	X		
nasal swab						
Pill count				X		

^{*}If staff are willing and able to do their own nasal swab, then visits will be remote. Consents and questionnaires will be returned by mail or fax, or collected at the LTCH. Pill bottles will be returned to a secure location at each LTCH to be collected by study staff.

¹For staff, nasopharyngeal/nasal swabs may be obtained on day 0-3, as they may not be obtained until the first time that the staff member attends at the LTCH to complete a shift. New staff starting work during the outbreak will be requested to have a swab on the first day that they work.

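### The pregnancy test and contraception check are tied to enrollment, not to the first dose, so an outdated check before study drug is not ruled out for women under 55 who may be enrolled before an outbreak

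*Protocol*

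**What the plan says.** Section 7.2.2 (exclusion criteria for residents and staff) reads, for females under 55: "negative urine pregnancy test at enrollment, and either menopause or two concurrent reliable methods of contraception need to be confirmed". The contraception check has no date of its own, and neither check has a maximum interval to the first dose.

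Section 6.1 gives two alternative times for the assessment of contraindications: "Either pre-study, or at baseline (identification of the outbreak), residents and staff will be assessed for contraindications to enrollment".

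Section 7.3 describes a first consent stage, which starts five calendar days after the fact sheet, and says: "LTCH staff and competent residents who provide written informed consent or e-consent at this stage may be enrolled into the trial". It then provides for the other case: "if written informed consent or e-consent has not been obtained prior to an outbreak being declared, informed consent will occur in two stages". The first stage can therefore precede an outbreak. Staff who join the unit during an outbreak are "referred to the trial for consenting and enrolment on an ongoing basis".

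At Day 0, section 13.2 has the coordinator review each "chart and medication record to assess eligibility; if possible, this will be performed remotely". Table 2, the staff schedule of events, marks an eligibility assessment at Day 0. Its footnote allows that if "staff are willing and able to do their own nasal swab, then visits will be remote". Neither place mentions a pregnancy test or contraception.

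Section 10.1.7 lists pregnancy under this introduction: "For the purpose of this trial, the following are exclusion criteria for study drug administration". It does not say when pregnancy is to be tested for.

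**The concern.** A pregnancy test protects only if it is recent when the drug is started. Here it is anchored to enrollment, and the trial is built so that consent, and possibly enrollment, can be completed while a home waits for an outbreak. For a woman enrolled in that waiting period, the date of the first dose depends on when an outbreak occurs, and the text puts no limit on the wait.

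The stake is fetal exposure. Sections 10.1.2 and 11.1 call favipiravir contraindicated in pregnancy, and 10.1.2 gives potential teratogenicity as the reason. Sections 8.1 and 11.1 stop the drug only once a pregnancy is known. Section 8.1 describes pregnancy as very unlikely, but it argues from the age of residents, and staff also take the drug. This is a point of participant safety. It does not touch the power or the analysis.

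**Working it through.** There is no figure in the plan to reproduce. The check is to set the provisions side by side and ask whether any of them forces a recent test.

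**Step 1. When can enrollment happen?**
- *At the outbreak.* Section 7 speaks of enrolling in units that have outbreaks. Section 7.1.1, item 4, makes a declared outbreak an entry condition for the home. Section 7.1.3 asks for expected shifts during the outbreak, which is hard to judge before one exists. On this reading the test falls at about Day 0, and the interval to the Day 1 dose is 1 − 0 = 1 day.
- *Before the outbreak.* Section 7.3 says that first-stage consenters may be enrolled, and the sentence that follows on missing consent shows that this stage can come before the outbreak. On this reading the interval is the waiting time to an outbreak plus the start-up time, with no stated maximum.

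**Step 2. Does a later step force a re-check on the second reading?**
- Table 2 has a Day 0 eligibility assessment but no row for a pregnancy test or contraception at any visit. It does have rows for swabs, questionnaires and pill count.
- Section 13.2 describes the eligibility step as a review of chart and medication record. For staff it adds an interview and diary and questionnaire tasks.
- The Day 1 dispensing steps (section 13.3, Baseline Visit) make no test result a condition of release.
- Section 10.1.7 bars the drug in pregnancy without a test date.
- The questionnaires (section 12.3) are not shown. A question about pregnancy would not replace a urine test.

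No provision forces a re-check. A Day 0 eligibility assessment could be taken to include it, but nothing says so.

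**Step 3. Who could be affected?**
- Residents: 16 units × at most 32 residents = 512. If the share under 65 given in section 8.1 (below 3%) holds in these units, 0.03 × 512 = 15.4, so at most 15 residents are under 65, of both sexes. Women under 55 are a subset of these. The realistic group is staff.
- Staff: the protocol does not give their sex, age or date of consent, so no count can be made.
- Staff who join during the outbreak are enrolled as they start, so their test falls near dosing and they are not affected.
- Allocation is 8 favipiravir units and 8 placebo units (section 9.1), so 8/16 = 50% of affected women would be expected to receive placebo.

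**Step 4. What exposure?** Under prophylaxis dosing (section 10.1.1), day 1 is 2 × 1600 = 3200 mg, then 2 × 800 = 1600 mg per day, in a course running to day 25.

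**The case against.** The strongest reply is that the protocol, read as a whole, places enrollment at the outbreak. Section 6.1 speaks of checking for contraindications to enrollment, a step that comes before enrollment and can be followed by a urine test when enrollment takes place. The wording in 7.3 says who may be enrolled and does not clearly say when, and the fact sheet speaks of contact in the event of an outbreak. In section 13.2 the consent step applies only if consent is missing, whereas the eligibility step carries no such condition, so early consent does not waive the Day 0 assessment. A physician confirms eligibility, and pregnancy is a listed exclusion. Pregnancy also separately bars drug administration under 10.1.7, and the two-method rule lowers the risk in any case.

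Most of this stands. The gap is one permitted reading of the text and not its plain meaning. Calling Table 2 and section 6.1 contradictory would go too far, because an overview that offers two time points, one of which the schedule adopts, is loose wording. What the reply does not supply is any sentence that puts the test or the contraception check at Day 0 or ahead of dispensing. For a teratogenicity safeguard, a site should not have to infer it, least of all where the staff visit is remote.

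**Conclusion.** The point holds as a safety gap in the wording. Sections 6.1, 7.2.2 and 7.3 taken together do not exclude a woman under 55 starting study drug on an outdated pregnancy test and contraception check. It rests on two assumptions: that some staff are enrolled on consent given before an outbreak, and that the Day 0 eligibility assessment is carried out without repeating the urine test. The protocol allows both and requires neither.

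The size is unknown. The protocol supports no headcount, event rate or typical interval, and about half of those affected would be on placebo.

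A reader might infer that checks up to 174 days old are to be expected, by counting the enrollment period from 10 May to 31 October 2020 (21 + 30 + 31 + 31 + 30 + 31 = 174). The documents do not support that as the magnitude. It would need a woman enrolled on the first day whose unit starts drug on the last, and it begins before version 2.0 is dated (4 June 2020). A reader might also infer that the protocol plans for early enrollment without re-assessment. It does not: the schedule and sections 7, 7.1.1 and 7.1.3 point the other way.

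**What to change.** Keep early consent, which speeds the start of prophylaxis, and change the timing of the checks:

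- In 7.2.2, replace the reference to enrollment with a requirement that both the urine test and the contraception confirmation be done at Day 0 or later and before the first dose.
- In 6.1, state that any contraindication check made pre-study is re-confirmed at Day 0.
- Add the test and the contraception check to Table 2, and to the resident schedule for any female resident under 55, as a condition of dispensing. For remote staff visits, require a documented self-test result before drug is released.

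The cost is protocol wording, a schedule row and a urine test that is already required, now placed at a Day 0 contact that already exists. The downsides are a few repeated tests where an early one was done and a possible slight delay to the first dose for some staff, mainly those seen remotely.

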6.2. Primary objective

The primary objective of this trial is to evaluate the efficacy of favipiravir compared with placebo as chemoprophylaxis for control of outbreaks of COVID-19 in LTCHs.

6.3 Secondary objectives

Secondary objectives are to compare the following secondary outcomes between study arms:

- 1. The proportion of residents of included LTCH units who die up to day 40, and up to day 60
- 2. The proportion of residents of included LTCH units who were uninfected at baseline and develop new symptomatic microbiologically confirmed COVID-19 up to day 40
- 3. The proportion of exposed staff uninfected at baseline in whom SARS-CoV-2 infection is identified up to day 14 and up to day 40
- 4. The proportion of residents of included LTCH units hospitalized up to day 40
- 5. The proportion of residents of included LTCH units who discontinue study medication due to adverse events
- 6. The proportion of LTCH staff of included LTCH units who discontinue study medication due to adverse events.
- 7. The occurrence of new microbiologically confirmed COVID-19 infections in residents in other units of the facility up to day 40 (dichotomous, at LTCH level)
- 8. The proportion of previously unaffected LTCH units of the remainder of the facility in which a case of COVID-19 is identified
- 9. The proportion of residents in the remainder of the facility who develop COVID-19 infections up to day 40

6.4 Endpoint Assessment

The primary outcome (primary endpoint) will be control of outbreak, defined as no new cases of COVID-19 in residents for 24 consecutive days up to day 40 after the start of prophylaxis. This outcome is dichotomous (yes/no) and will be determined at the level of the cluster (LTCH unit).

Secondary outcome measures (endpoints) are:

- 1. The proportion of residents of included LTCH units who die up to day 40, and up to day 60
- 2. The proportion of residents of included LTCH units who were uninfected at baseline and develop new symptomatic microbiologically confirmed COVID-19 up to day 40
- 3. The proportion of exposed staff uninfected at baseline in whom SARS-CoV-2 infection is identified up to day 14 and up to day 40
- 4. The proportion of residents of included LTCH units hospitalized up to day 40
- 5. The proportion of residents of included LTCH units who discontinue study medication due to adverse events
- 6. The proportion of LTCH staff of included LTCH units who discontinue study medication due to adverse events.
- 7. The occurrence of new microbiologically confirmed COVID-19 infections in residents in other units of the facility up to day 40 (dichotomous, at LTCH level)
- 8. The proportion of previously unaffected LTCH units of the remainder of the facility in which a case of COVID-19 is identified
- 9. The proportion of residents in the remainder of the facility who develop COVID-19 infections up to day 40

